**Table 3 Gross anatomy, cystic and fibrotic volumes, in Pkd2ws25 -/- mice**

Parameters	Control	OCT	PAS	OCT vs control		PAS vs control		OCT vs PAS	
				p	% change	p	% change	p	% change
Body wt (g):	31.60±3.57	33.76±2.49	33.92±1.53	NS	6.8	NS	7.3	NS	0.5
Liver wt (g):	3.60±0.47	2.76±0.18	2.65±0.12	0.05	-23.3	0.05	-26.4	NS	-3.9
Liver wt (% bw):	11.57±1.21	8.35±0.73	7.62±0.53	0.02	-27.9	0.01	-34.1	NS	-8.7
Kidney wt (g):	0.65±0.09	0.56±0.04	0.55±0.06	NS	-13.5	NS	-14.2	NS	-0.8
Kidney wt (% bw):	2.08±0.14	1.69±0.11	1.59±0.08	0.03	-18.6	0.008	-23.7	NS	-6.2
Hepatic cystic area	41.55±4.73	29.75±2.53	23.24±1.16	0.03	-28.4	0.0007	-44.1	0.03	-21.9
Hepatic fibrotic area	2.29±0.16	1.77±0.12	1.39±0.09	0.02	-22.5	0.0001	-39.5	0.003	-21.7
Renal cystic area	31.83±2.85	23.69±2.15	20.24±1.99	0.002	-25.6	0.0001	-35.6	0.03	-13.5
Renal fibrotic area	1.49±0.11	1.23±0.04	1.06±0.06	0.0006	-18.0	0.0001	-29.5	0.003	-14.1

**Figure 1: Role of octreotide (OCT) and Pasireotide (PAS) treatment in hepatic cystogenesis.** Our experimental data suggest that expression of SSTR1, 2 and somatostatin level are decreased in cystic cholangiocytes that results in cAMP elevation and activation of the cellular processes involved in hepatic cystogenesis. However, the expression of SSTR3, 4 and 5 did not change. Thus, treatment of cystic cholangiocytes with OCT (binds to SSTR2, 3 and 5) or PAS (binds to SSTR1, 2, 3 and 5) should lead to cAMP inhibition and decreased growth of hepatic cysts.

**Figure 6 Role of octreotide (OCT) and Pasireotide (PAS) treatment in hepatic cystogenesis.** Our experimental data suggest that expression of SSTR1, 2 and somatostatin (SST) level are decreased in cystic cholangiocytes that results in cAMP elevation and activation of the cellular processes involved in hepatic cystogenesis. However, the expression of SSTR3, 4 and 5 did not change. Thus, treatment of cystic cholangiocytes with OCT (binds to SSTR2, 3 and 5) or PAS (binds to SSTR1, 2, 3 and 5) should lead to cAMP inhibition and decreased growth of hepatic cysts.

**2 Study Rationale/Purpose**

Pasireotide (SOM230) is a novel multi-receptor-targeted analog that has high affinity for four of the five SST receptor subtypes (SSTR1, SSTR2, SSTR3 and SSTR5); it has a 40-fold higher affinity and 158-fold higher functional activity for the SSTR5 receptor than octreotide. Because of its broad receptor binding profile, pasireotide may be more potent in PLD than octreotide. In this randomized double blind placebo controlled trial we will compare SOM230 treatment to placebo for 12 months in patients with PLD. The primary endpoints will be assessed at 12 months and patients receiving placebo then crossed over to SOM230, permitting all participants to receive SOM230 for the subsequent two years. MRI will be used to assess liver volume – the primary endpoint, which will be assessed at baseline, end of years 1 and 3. This study will assess the efficacy and safety of SOM230 in reducing total liver volume and improving quality of life over 12 months (we will not be assessing efficacy at 24 months. The therapy way be effective in PLD but also may prove to be effective for many more patients with PKD which will be evaluated using eGFR and kidney volume using MRI.

## **2.1 Selection of doses**

Patients will be treated with SOM-230 (pasireotide LAR) 60mg IM once every 28 days or placebo year 0-1. All participants will receive pasireotide LAR years 2 and 3. Each cycle is  $28 \pm 2$  days. There will be no dose titration above the 60mg dose but there may be dose reduction to 20mg if patients do not tolerate 60mg or 40mg.

## **2.2 Placebo dose**

The placebo dose will be monitored and adjusted monthly in a similar fashion.

## **3 Objectives**

### **3.1 Primary objectives**

The primary objectives of this study will be to evaluate the absolute and percent changes in liver volume from baseline to month 12 in the treatment arm compared to the placebo arm. We will also evaluate the adverse events throughout the length of the study and as reported at 12 and 36 months of treatment.

### **3.2 Secondary objectives**

Absolute and percent changes in liver volume in the placebo group before (year 1) and after (years 2-3) cross-over to active treatment

Absolute and percent changes in liver volume in the treatment arm during years 2-3 compared to the placebo arm during year 1

Changes in eGFR from baseline (or from month 3) at 12 and 36 months in individuals with ADPKD

Changes in kidney volume from baseline at 12 and 36 months in individuals with ADPKD

Symptoms at baseline, 12 and 36 months. Changes in symptoms, measured by SF36-questionnaire QOL-questionnaire

Quality of Life at baseline, 12 and 36 months. Changes in quality of life, measured by SF36-questionnaire (SF-36v2™)

Responders at 12 and 36 months.

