#### 6.2 Treatment arms

There will be stratified randomization for PLD patients with ADPLD and ADPKD (see Table 5):

All participants who receive the placebo during year one will be given the option to continue on study to receive active study drug for years two and three. Thus, all participants will be receiving SOM230 years two and three.

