#### **7.4.1.2 Secondary efficacy assessments**

Absolute and percent changes in liver volume in the placebo group before (year 1) and after (years 2-3) cross-over to active treatment will be assessed based on comparison of baseline volumes as assessed by MRI/CT in each subject. The measurements will be performed in the Biomedical imaging core facility by blinded assessors. Similarly, absolute and percent changes in liver volume will be assessed in the treatment arm during years 2-3 compared to the placebo arm during year 1. Similarly, changes in kidney volume from baseline at 12 and 36 months in individuals with ADPKD will be assessed by MRI.

Changes in eGFR, vital signs, creatinine, liver function tests, APTT, PT, glucose values from baseline (or from month 3) at 12 and 36 months in all individuals and treated as a continuous variable. Data from ADPLD patients will be excluded from the renal outcome sub-analyses.

Measurement of Effect (Subjective Response):

Changes in quality of life at baseline and 12 and 36 months will be measured by SF36-questionnaire QOL-questionnaire (SF-36v2™).

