### 10.2 Statistical methods

Demographics and laboratory data will be plotted (e.g. box plots) and summarized by treatment group. Frequency distributions will be used to describe categorical values and basic summary statistics (mean, standard deviation, median, and inter-quartile range) used to describe continuous values. All tests will be two-sided with alpha level 0.05. For quantitative endpoints (e.g. change in kidney and liver volumes, renal function, and SF-36 scales) the two-group independent samples t-test will be used to test for an effect of treatment. Should the assumptions of normality and equality of variances be untenable, we will consider a data transformation or use of the Wilcoxon rank sum test. Both point estimates (mean) and 95% confidence intervals will be used to summarize treatment effects. For qualitative endpoints (e.g. presence or absence of response) we will compare treatment groups using the chi-square or Fisher's exact test as appropriate.

**Efficacy (Liver & kidney):** The primary analysis of treatment efficacy will follow intent-to-treat principles, attempting to include all randomized patients. For the primary endpoint (change in

liver volume) we will not be able to include anyone without a 12 month MRI (kidney volumes will be handled in the same way). For the “response” endpoints, those without a 12 month MRI will be included in the analysis as non-responders. Secondary analysis – Efficacy (QOL): We will have up to 5 longitudinal assessments of QOL for each patient. Repeated measures analysis of variance will be used to compare mean QOL profiles over time between treatment groups. Also, within patient rates of change or slopes in QOL measures will be estimated (using simple linear regression) and compared between groups using the two-sample t-test.

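### Two secondary analyses run past the month-12 crossover without allowing for it: a 24-month liver-volume change is compared with a 12-month one, and the between-arm QOL slope test has no month-12 cut-off

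*Combined protocol and SAP*

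**What the plan says.** **Liver volume.** Section 3.2 sets two objectives that cross month 12. One is between arms: "Absolute and percent changes in liver volume in the treatment arm during years 2-3 compared to the placebo arm during year 1". The other is within the placebo group: "Absolute and percent changes in liver volume in the placebo group before (year 1) and after (years 2-3) cross-over to active treatment". Section 7.4.1.2 repeats the first ("will be assessed in the treatment arm during years 2-3 compared to the placebo arm during year 1"). Section 2 fixes the imaging times for liver volume, "which will be assessed at baseline, end of years 1 and 3", and Section 4 agrees; there is no month-24 scan. Section 10.2 gives a general independent-samples t-test for change in liver volume, with a transformation or the Wilcoxon test as fallback. Neither objective is put on a yearly scale.

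**Quality of life.** Section 10.2 states "We will have up to 5 longitudinal assessments of QOL for each patient". It plans a repeated-measures comparison of profiles between treatment groups, and then: "within patient rates of change or slopes in QOL measures will be estimated (using simple linear regression) and compared between groups". No time window is given for either. Section 6.2 says of the extension: "Thus, all participants will be receiving SOM230 years two and three". Section 2 frames the efficacy question as "reducing total liver volume and improving quality of life over 12 months". Section 3.3, the tertiary objective, assigns change after month 12 to a description by treatment sequence.

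**The concern.** In both analyses the number produced is not the effect a reader would take it for.

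For liver volume, the contrast combines drug effect with interval length. The treated arm has twice as long to grow, or to shrink, as the placebo arm it is compared with. The placebo before/after contrast has the same imbalance. It is also a within-patient comparison, which the general two-sample test does not suit.

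For QOL the two arms share one time axis, so the fault is different. After month 12 both arms receive SOM230, and a straight line fitted through a placebo patient's whole record averages placebo and active time. The difference in slopes then no longer estimates SOM230 against placebo.

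Section 6.4 provides for unblinding at the year-1 database lock. If the scale and the window are left open, they would be chosen after the year-1 result is known.

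**Working it through.** The plan states no power or expected value for either analysis, so there is no figure of its own to reproduce. The 80% power in Section 10.2 concerns the primary endpoint.

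**Liver volume: inputs.** Untreated growth is 5% per year with SD 3 (Section 10.2), or 0.9% with SD 8.35 in the prior trial's placebo group (Section 1.5.2.2). Octreotide's second-year change was -0.77%, and the crossed-over placebo patients changed by -7.66% in their first year on drug (both Section 1.5.2.2).

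*Formula.* At yearly rate g, the 24-month change is (1+g)² - 1.

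- Drug halves growth, 0.9% untreated: 1.0045² - 1 = 0.90%, against 0.9% on placebo. Apparent effect nil; true effect -0.45 points per year.
- Drug halves growth, 5% untreated: 1.025² - 1 = 5.06%, against 5%. Apparent effect nil; true effect -2.5 points per year.
- Volume keeps falling at -0.77% per year: 0.9923² - 1 = -1.53%. Raw contrast: -1.53 - 0.90 = -2.43 points. Yearly contrast: -0.77 - 0.90 = -1.67 points. Ratio 2.43/1.67 = 1.46.
- Inert drug, 0.9%: 1.009² - 1 = 1.81%, an artefact of 0.9 points. With 30 and 15 patients and SD 8.35, a simulated t-test rejects in about 2-6% of trials, which is negligible.
- Inert drug, 5%: 1.05² - 1 = 10.25%, an artefact of 5.25 points. Rejection is 92% to over 99% at SD 3, and 18-56% at SD 7.72 (the SD that gives 80% power for 7 points with 30 and 15 patients).

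The rejection ranges cover a 24-month SD of 1 to 2 times the 12-month SD, and pooled or unequal-variance tests. The multiplier is an assumption.

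**QOL: which visits.** At most three assessments fall by month 12 (screening, month 6, month 12), so a fourth or fifth must follow the crossover. The Table 8 row shows seven marks and its columns are misaligned in the available text, Section 10.2 says up to five, and Section 3.2 names three times. Visit times are therefore assumptions, as is the time course.

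*Formula.* A least-squares slope is Σ(t - mean t)·y / Sxx, where Sxx = Σ(t - mean t)². Let D be the full benefit. With linear accrual, benefit grows by D per year on drug. With a plateau, it reaches D after 12 months on drug and stays there. Placebo patients start the same course at month 12.

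*Worked case, months 0/6/12/24/36* (0, 0.5, 1, 2, 3 years; mean 1.3; Sxx 5.80):

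- Linear: the arm differences are 0, 0.5, 1, 1, 1, so the slope difference is (-0.4 - 0.3 + 0.7 + 1.7)/5.80 = 0.293.
- Plateau: the arm differences are 0, 0.5, 1, 0, 0, so it is (-0.4 - 0.3)/5.80 = -0.121.

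| Visits (months) | Sxx (years²) | Linear, D/yr | 12-month plateau, D/yr | Linear difference × √Sxx |
|---|---|---|---|---|
| 0/6/12 | 0.50 | 1.000 | 1.000 | 0.71 |
| 0/12/36 | 4.67 | 0.286 | -0.071 | 0.62 |
| 0/12/24/36 | 5.00 | 0.300 | -0.100 | 0.67 |
| 0/6/12/24/36 | 5.80 | 0.293 | -0.121 | 0.71 |
| every 6 to 36 | 7.00 | 0.286 | -0.143 | 0.76 |
| 0/6/12/24/30/36/39 | 9.63 | 0.247 | -0.143 | 0.77 |
| 0/6/12/18/24 | 2.50 | 0.500 | 0.000 | 0.79 |

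The last column is signal-to-noise with independent errors. On 0/6/12/24/36 the plateau difference is -0.040 if the plateau comes at 18 months, 0 at 24 months and +0.059 at 30 months, so reversal there needs a plateau before about 24 months.

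**Repeated measures.** In the worked plateau case the year-1 separation stays visible in the profile. The mean arm difference over post-baseline visits falls from (0.5 + 1)/2 = 0.75 D to (0.5 + 1 + 0 + 0)/4 = 0.375 D.

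**The case against.** - *The intervals are labelled.* Sections 3.2 and 7.4.1.2 name them, and nothing calls the result a yearly effect. This stands as far as it goes: the overstatement needs a reader to take the contrast as yearly. It does not help with the drug that halves growth, where the labelled contrast still shows nothing.
- *An analysis is already provided.* The t-test in Section 10.2 would cover the between-arm contrast, so it would be wrong to say that no test exists. Section 7.4.1.2 also ties the placebo before/after assessment to each subject's own volumes, which points towards pairing but names no paired method.
- *An ineffective drug would not reach month 36.* A reader might infer from the 5.25-point artefact that the plan would probably declare an inert drug harmful. The documents do not support that. Section 6.10 ends the extension if year 1 shows no efficacy, and Section 7.4.2 ties it to growth below 2% per year. Sections 4.1 and 6.2 state the extension without that condition, and the passages should be reconciled. The 5% inert case is illustrative only.
- *Annualising also distorts.* This stands. A fall of -7.66% followed by -0.77% gives 0.9234 × 0.9923 = 0.9163, and ln(0.9163)/2 is about -4.4% per year, well short of the first-year effect. An annualised rate alone is not enough.
- *The QOL intent is already clear.* Sections 2 and 3.3 do point to a 12-month comparison with later change by sequence. Neither sets a window for the tests in Section 10.2. Section 8 separates years 2 and 3 explicitly for adverse events; nothing equivalent is said for QOL.
- *The QOL reversal is small.* This also stands. If D equals one within-patient SD (an assumption), the standard error of the slope difference on 0/6/12/24/36 is (1/√5.80) × √(1/30 + 1/15) = 0.131, so z is about -0.121/0.131 = -0.9. A false signal of harm should not be inferred.

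**Conclusion.** The point holds for two secondary analyses and should be corrected. The liver contrast compares 24 months with 12. It hides a halving of growth at either growth rate in the documents, and it overstates a continuing fall by about 46% (0.76 points, against prior-trial SDs of about 7 to 8) if read as yearly. Of the two halving cases, only the 0.9% one stays under the 2% per year in Section 7.4.2.

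The QOL slope difference is biased as an estimate of the year-1 effect. On the assumed schedules reaching month 36 it is 0.25-0.30 of the year-1 value with linear accrual, and zero or slightly negative with an early plateau. A reader might infer a loss of power as well. Under linear accrual signal-to-noise is the same on 0/6/12 and 0/6/12/24/36 and similar on the other schedules, so the harm there is a biased estimate, not lost power. The repeated-measures test has the same missing window but is less affected because it imposes no straight line.

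The primary month-12 liver analysis and the month-12 SF-36 t-test are unaffected, so nothing here bears on the trial's main conclusion. The QOL figures rest on assumed visit times and time courses; the liver figures assume a constant yearly rate.

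**What to change.** **QOL.** In Section 10.2, limit the between-arm slope and repeated-measures tests to baseline, month 6 and month 12. Report later visits by treatment sequence, as Section 3.3 intends. State which visits in Table 8 are used.

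**Liver volume.** For year 1 against years 2-3, report the annualised log change (log of the volume ratio divided by the years between scans) together with the raw change and its interval length. Use a test that allows unequal variances. State that the annualised rate averages over a possible early fall and plateau, as in the prior octreotide data in Section 1.5.2.2. Analyse the placebo before/after contrast as paired within patient.

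**Cost.** The change is to wording only, with no new data, and is best made before the year-1 unblinding. There are two downsides. A slope from months 0/6/12 has a standard error 3.4 times that from 0/6/12/24/36 (1.414/0.415, from 1/√Sxx); under linear accrual the effect is also 3.4 times larger, and with an early plateau the restriction is a gain. A 24-month average rate can understate a first-year effect, which is why the raw change must stand beside it.

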### **3.3 Tertiary objective**

Longitudinal changes beyond 12 months in above factors, stratified by treatment sequence.

## **4 Study design**

This study will be conducted over 3 years as a randomized, double-blind control, clinical trial through year 1, followed by an open-label extension phase for the subsequent 2 years. Screening and randomization visits will take place at Mayo Clinic and patients will then be followed by Mayo Clinic for three years. We will monitor the patients with blood and urine tests on days 22, 29, 50, 57 and 89 and then at Months 6, 9, 12, 15, 18, 24, 27, 30, 33 and 36. Follow up visits will occur at one and three months post last dose of study drug. For patients who received placebo during year one, the labs on days 22, 29, 50, 27 and 85 will be repeated as these are safety labs. All patients will be required to undergo MRI or CT scan imaging at the baseline, 12 month (end

of year 1) and 36 month (end of year 3) visits to fulfill the primary study endpoints. Safety monitoring with ECG, Hemoglobin A1C, liver function and glucose testing will be performed locally at the study sub-sites and monitored centrally by study staff at Mayo Clinic.

Patients will be recruited during visits to the Department of Nephrology and Hypertension

Patients who had participated in previous studies will also be contacted as long as they meet all eligibility criteria. We will also recruit through [clinicaltrials.gov](http://clinicaltrials.gov) ( <http://clinicaltrials.gov> ), Mayo Clinic Trials website ( <http://clinicaltrials.mayo.edu/> ) and PKD foundation clinical trials ( <http://www.pkdcure.org/Research/ClinicalTrials/ActiveRecruiting.aspx> ) listed on the web . Patients who contact the study coordinator will be given information regarding the study and participation. The study coordinator will screen those interested and proceed with the study design for all patients who would like to participate.

#### **4.1 Treatment**

Forty-eight patients with severe PLD identified at a single Center, Mayo Clinic, Rochester, MN will be stratified with randomization in a 2:1 allocation to SOM230 or placebo in year 1, in this study. All participants will be offered SOM230 in years 2 and 3. Recruitment of patients is expected to occur relatively rapidly (over the first 6 months) as a result of the Mayo Clinic's large referral base for patients with ADPKD and ADPLD and we have more than 140 patients who wish to be notified if clinical trials with SST analogs for PLD become available.

#### **4.2 Follow-up**

Follow up will continue until 3 months after last injection to monitor hemoglobin A1C.

#### **4.3 Treatment extension**

No further treatment extension is planned beyond the three years of this protocol.

### **5 Population**

#### **5.1 General criteria**

A total of 48 patients (45 + 3 to allow for dropouts) with severe PLD with either autosomal dominant polycystic kidney (ADPKD) or autosomal dominant liver disease (ADPLD) will be enrolled. To enroll a patient, call [REDACTED]. Study personnel will check patient eligibility and the existence of a signed consent form before treatment is begun.

Limited Travel reimbursement is provided. Costs of tests obtained for the sole purpose of this study will be defrayed from study funds. Costs of tests necessary for patient's usual evaluation and management will be borne by patient and his/her health coverage. Pasireotide-LAR safety data, the absence of other medical treatment modalities for this group of patients, and preliminary experimental and clinical observations justify such a study. Patients must meet all criteria listed below. The investigator or her designee must ensure that all patients who are offered enrollment in the study meet all of the following inclusion and exclusion criteria. This will be a single center study at Mayo Clinic, Rochester, MN.

## 5.2 Inclusion/exclusion criteria

The investigator or her designee must ensure that all patients who are offered enrollment in the study meet all of the following inclusion and exclusion criteria:

### 5.2.1 Inclusion criteria

Male or female Age  $\geq$  18 years.

Diagnosis of PLD associated with ADPKD (meeting the Modified Ravine's criteria) or isolated ADPLD (defined by the criteria described by Reynolds et al).

Severe PLD defined as a liver volume  $>4000$ mL or symptomatic disease due to mass effects from hepatic cysts (must be able to undergo MRI or CT scan to determine this).

Not a candidate for or declining surgical intervention.

Capable of providing informed consent.

Life expectancy  $\geq 12$  weeks

Patients with a known history of impaired fasting blood glucose (glucose  $>100$  and  $<126$ ) may be included at the discretion of the PI. These patients should be monitored closely throughout the trial and anti-hyperglycemic treatment adjusted as necessary. Patients that are deemed non eligible due to elevated glucose can be re-screened after adequate medical treatment.

Adequate end organ function as defined by:

Adequate bone marrow function:

- WBC  $\geq 2.5 \times 10^9$ /L
- Absolute Neutrophil Count (ANC)  $\geq 1.5 \times 10^9$ /L
- Platelets  $\geq 100 \times 10^9$ /L
- Hb  $\geq 9$  g/dL

No evidence of significant liver disease:

- Serum bilirubin  $\leq 1.5 \times$  ULN
- INR  $< 1.3$
- ALT and AST  $\leq 2 \times$  ULN

Estimated glomerular filtration rate (eGFR)  $>30$  ml/min/m^2

Serum amylase and lipase  $\leq 1.5 \times$  ULN

Alkaline phosphatase  $\leq 2.5 \times$  ULN

Written informed consent obtained prior to any screening procedures

Willingness and ability to comply with scheduled visits, treatment plans, laboratory tests and other study procedures

